8.4.3.2 Duration of Response

The duration of overall response will be evaluated by dose level and overall enrollment. The duration of overall response is measured from the time measurement criteria are met for CR or PR (whichever is first recorded) until the first date that recurrent or PD is objectively documented (taking as reference for PD the smallest measurements recorded since the treatment started).

8.4.3.3 Progression-Free Survival

PFS will be evaluated by dose level and overall using Kaplan-Meier methods. PFS will be defined as the time from the date of first treatment to the date of disease progression or death (any cause) whichever occurs first. Subjects who do not have disease progression or have not died at the end of follow up will be censored at the last known date the subject was progression free.

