6.3.7 Progression-Free Survival (PFS)

PFS is defined as the duration of time from start of treatment to time of progression or death, whichever occurs first.

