8.4.3 Analyses of Secondary Endpoint

Analyses of secondary endpoint to obtain preliminary data on objective response rate (ORR), disease control rate (DCR), duration of response, progression-free survival (PFS), and overall survival (OS) in treated subjects.

Since this is a Phase I trial, only preliminary data will be obtained for evidence of vaccine efficacy. Preliminary analyses of vaccine efficacy are described in the Sections [8.4.3.1](#) to [8.4.3.4](#) below.

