8.4.3.4 Overall Survival

OS will be evaluated by dose level and overall using Kaplan-Meier methods. OS will be defined as the time from the date of first treatment to the date of death (any cause). Subjects who are alive at the end of follow up will be censored at the last known date alive.

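### The PFS censoring sentence in 8.4.3.3 joins its two conditions with 'or', so read literally it contradicts the PFS definition; a minor wording fix resolves it

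*Combined protocol and SAP*

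**What the plan says.** Section 6.3.7: "PFS is defined as the duration of time from start of treatment to time of progression or death, whichever occurs first". Section 8.4.3.3 gives the same event, ending at "the date of disease progression or death (any cause) whichever occurs first", and states that "PFS will be evaluated by dose level and overall using Kaplan-Meier methods".

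The next sentence of 8.4.3.3 sets the censoring rule: "Subjects who do not have disease progression or have not died at the end of follow up will be censored". The censoring date is the last known date without progression. This is the only PFS censoring rule in the document; 6.3.7 has none. The OS rule in 8.4.3.4 has a single condition and is clear: "Subjects who are alive at the end of follow up will be censored at the last known date alive".

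On the weight given to these analyses, 8.4.3 says: "Since this is a Phase I trial, only preliminary data will be obtained for evidence of vaccine efficacy".

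**The concern.** If the event is progression or death, the subjects to censor are those with neither. The sentence instead describes anyone lacking at least one of the two. Two groups that are events under the definition become censored: subjects alive after progression, and subjects who died without documented progression.

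The first group could be sizeable here. Progression ends protocol therapy (3.7.1), but the study calendar in 3.5 continues survival contact for years, and 8.1 places the preliminary efficacy look around two years after trial start. A programmer who followed the sentence word for word would produce a PFS curve with too few events, and those subjects would be censored at a date before their event. Section 8.4.8 says that no individual participant data will be tabulated, so a reader of the results could not easily detect it.

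**Working it through.** The plan states no PFS figure, so there is nothing to reproduce. The check has three parts.

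**1. Logic.** Let P = progressed and D = died. The definition makes an event of (P or D), so the matching censored set is (not P and not D). The sentence censors (not P or not D), which equals not (P and D).

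| State at end of follow-up | By the definition | By the sentence, literally |
|---|---|---|
| No progression, alive | censored | censored |
| No progression, died | event | censored (conflict) |
| Progressed, alive | event | censored (conflict) |
| Progressed, died | event | event |

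Two of the four states conflict.

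**2. Three hypothetical records**, using the scan weeks in 6.3.1 (week 6, then every 8 weeks):

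- A: progression at week 14, alive. Definition: event at week 14. Literal: censored at the week 6 scan.
- B: death at week 20, no progression. Definition: event at week 20. Literal: censored at the week 14 scan.
- C: progression at week 14, death at week 40. Event at week 14 under both.

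Kaplan-Meier by the definition: at week 14 there are 3 at risk and 2 events, so S = 1 − 2/3 = 0.33; at week 20, S = 0. Literal: A has left the risk set, so at week 14 there are 2 at risk and 1 event, and S = 1 − 1/2 = 0.50, where it stays.

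**3. Illustrative size.** From the documents: the scan schedule (6.3.1); 10 to 16 treated subjects (8.2: 6 to 12, plus 4); a look at about 24 months (8.1); contact after therapy for 12 + 24 + 24 = 60 months (3.5, follow-up footnote). Assumed, not in the documents: exponential times; median time to progression 2, 4 or 6 months; median survival after progression 6, 9 or 18 months; median time to death without progression 24 months; 12 months of uniform accrual. For the long case, each subject is followed for 60 months from first dose. Mean PFS events per 10 subjects, with share lost = 1 − literal/definition:

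| Median months: to progression / survival after it | 24-month look: definition, literal, lost | 60 months: definition, literal, lost |
|---|---|---|
| 2 / 6 | 9.97, 7.07, 29% | 10.00, 8.97, 10% |
| 2 / 18 | 9.96, 3.76, 62% | 10.00, 7.95, 20% |
| 4 / 9 | 9.61, 4.80, 50% | 10.00, 8.21, 18% |
| 6 / 6 | 9.07, 4.93, 46% | 10.00, 7.76, 22% |
| 6 / 18 | 9.06, 2.52, 72% | 10.00, 6.71, 33% |

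Across all nine combinations the loss is 29 to 72% at 24 months and 10 to 33% at 60 months.

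As a variant, death was made independent of progression, with median OS of 11 or 13 months (the medians that 1.2.6.3 reports for the single-agent study) and median time to progression of 2 or 4 months. The loss is then 53 to 64% at 24 months and 22 to 33% at 60 months.

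Under the first model at the 24-month look, mean 6-month PFS moves from 0.14–0.15 to 0.23–0.43 (median time to progression 2 months), from 0.35 to 0.49–0.67 (4 months) and from 0.47 to 0.62–0.78 (6 months). The typical median PFS stays at 3.2 months in the two mildest combinations (2 / 6 and 2 / 9) and is not reached in the most extreme (6 / 18).

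**The case against.** The strongest reply is that nobody would apply the sentence this way. The definition stands immediately before it and 6.3.7 repeats it. The censoring date, "will be censored at the last known date the subject was progression free", suits subjects who are still free of progression. The OS rule beside it censors only subjects without the event. The literal reading would require both progression and death before PFS counts an event, which the two definitions exclude. This largely stands: the intended rule can be recovered, and any bias depends on literal programming.

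The second reply concerns size. The sentence speaks of the end of follow-up, and contact runs for about 60 months after therapy. By then most subjects who progressed have died and keep their event even under the literal rule. This also stands, and it is why the 60-month results appear beside the 24-month ones.

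The third is that little depends on PFS. It is secondary and descriptive, and no sample size, dose decision or halting rule uses it. That settles the severity.

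What remains is that two adjacent sentences disagree and nothing elsewhere says which governs.

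**Conclusion.** The censoring sentence is wrong as written: it conflicts with the plan's own PFS definition for subjects alive after progression and for subjects who died without it. That is a matter of logic and needs no assumption. Severity is minor.

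Three stronger readings are tempting, and the documents support none of them.

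- A reader might infer that reported PFS will be inflated. That follows only if the sentence is programmed literally, and the neighbouring text points the other way. Even then, upward bias is the expected direction, not a certainty at every time point: earlier censoring shrinks the risk set, so in a very small sample a later event can pull the curve down further.
- A reader might infer that half or more of the events would go. The illustrative loss is roughly 30 to 70% at 24 months and roughly 10 to 35% after about 60 months. These ranges rest on assumed event times, and the plan gives no expected PFS to narrow them.
- A reader might infer that median PFS must lengthen. It did not change in the mildest combinations, and the plan does not name the median as its summary.

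**What to change.** In 8.4.3.3, replace the censoring sentence with: Subjects who have neither progressed nor died by the end of follow-up "will be censored at the last known date the subject was progression free". The rule then matches the definition in all four states. The censoring date stays as it is, since no fault in it has been shown.

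The cost is one sentence in the statistical section, with no new data, visits or subjects.

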8.4.3.4 Overall Survival

OS will be evaluated by dose level and overall using Kaplan-Meier methods. OS will be defined as the time from the date of first treatment to the date of death (any cause). Subjects who are alive at the end of follow up will be censored at the last known date alive.

8.4.4 Safety Analysis

DLTs will be evaluated continuously in a dose level. An overall assessment of whether to de-escalate to the next dose level will be made at least 1 week after the last subject in the previous dose level has received their first injection. A dose level will be considered safe if $< 33\%$ of subjects treated at a dose level experience a DLT (i.e., 0 of 3, ≤ 1 of 6, ≤ 2 of 9, ≤ 3 of 10). Safety will be evaluated in 3 or 6 subjects at each dose level in the dose escalation component of the study. Safety will continue to be monitored among additional subjects treated at the MTD or HTD in the dose expansion component of the study. A subject will be considered evaluable for safety if treated with at least one injection. DLTs will be observed for 1 week.

Safety endpoints will be analyzed as summary statistics during treatment and/or as change scores from baseline assessments. AEs will be coded as defined in the Medical Dictionary for Regulatory Activities (MedDRA). All AEs will be recorded and tabulated following each treatment (vaccine injection). AEs will be recorded by severity, frequency, and relationship to the study intervention and will be presented by System Organ Class (SOC) designations and preferred term groupings. Information on each AE will include start date, stop date, severity, relationship, expectedness, outcome, and duration. Adverse events leading to premature discontinuation from the study intervention and serious treatment-emergent AEs will be presented either in a Table or a Listing.

In addition, overall safety will be assessed by descriptive analyses using tabulated frequencies of AEs by grade using CTCAE Version 5.0 within dose levels and for the overall study population in terms of treatment-emergent AEs, SAEs, and clinically significant changes in safety laboratory tests, physical examinations, ECGs, and vital signs.

The safety events listed in section [8.4.6.2](#) will trigger a temporary suspension of the study injections.:

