3.1.2 Dose De-Escalation

Up to six patients will be enrolled at dose level 1. If ≤ 1 of 6 patients experience a DLT, initiation of the dose expansion phase will occur. If ≥ 2 of 3 or 6 experience DLT in the initial dose level, then dose de-escalation will occur. Up to six patients will be enrolled at the lower dose level (-1) (1×10^{11} VP). If ≤ 1 of 6 patients experience a DLT, then the maximum tolerated (MTD) will be declared at this dose, and initiation of the dose expansion phase will occur. If ≥ 2 of 3 or 6 experience DLT at dose level -1, then an amendment may be written to evaluate a further dose de-escalation.

In the second part, dose expansion will occur when the MTD has been determined. An additional 4 subjects will be enrolled in the dose expansion component of the trial, for a total of 10 subjects treated at the MTD.

A schematic overview of the study is shown in Figure 6.

In the initial component of the study, 3 to 6 subjects will be sequentially enrolled starting at the standard dose at dose level 1. During enrollment at each dose level, there will be a minimum of 3 days between enrolling successive subjects. DLTs will be monitored continuously.

Dose levels are shown in Table 4. No intra-patient dose escalations are permitted.

Table 4: Dose Levels for Each ETBX VP

Dose Level (DL)	ETBX VP
Standard (1)	5×10^{11}
-1	1×10^{11}

[figure not shown]
Standard dose (DL 1) (5×10^{11} VP):

- If ≤ 1 of the initial 6 subjects experience a DLT, dose expansion will commence.
- If >1 of the initial 3 subjects, or if ≥ 2 of the 6 total subjects experience a DLT, enrollment at DL -1 will commence.

Dose de-escalation DL -1 (1×10^{11} VP):

- If ≤ 1 of the initial 6 subjects experience a DLT, this dose level will be defined as the MTD and dose expansion will commence.
- If >1 of the initial 3 subjects, or if ≥ 2 of the 6 total subjects experience a DLT, then a protocol amendment may be written to evaluate a further dose de-escalation..

Figure 6: Study Design and Treatment Schema

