8.2 SAMPLE SIZE DETERMINATION

Up to six patients will be enrolled in an initial dose level 1. If ≤ 1 of 6 patients experience a DLT, then the MTD will be declared, and initiation of the dose expansion phase will occur. If ≥ 2 of 6 experience DLT in the initial dose level 1, then dose de-escalation will occur. Up to six patients will be enrolled at the lower dose level (-1) (1×10^{11} VP). If ≤ 1 of 6 patients experience a DLT, then the maximum tolerated (MTD) will be declared at this dose, and initiation of the dose expansion phase will occur. If ≥ 2 of 6 (or ≥ 2 of the first 3) experience DLT in this second dose level -1, then an amendment may be written to further evaluate dose de-escalation. Once the MTD is identified, the dose expansion component will commence. An additional 4 subjects will be

enrolled at the MTD for a total of 10 subjects to gain additional safety data and exploratory data on vaccine immunogenicity.

We assume 16 patients will have screen failure. Therefore, up to 32 subjects will be enrolled in the study. Initial dose evaluation and or dose finding will require 6-12 subjects, followed by 4 additional subjects treated at a defined dose.

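### Section 8.4.4 counts 0 of 3 as safe, while the Précis and Sections 3.1.2 and 8.2 need at most 1 DLT in six: the dose-clearance rule must be reconciled

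*Combined protocol and SAP*

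**What the plan says.** Section 8.4.4 calls a dose level safe when fewer than 33% of its subjects have a DLT, and spells this out as "0 of 3, ≤ 1 of 6, ≤ 2 of 9, ≤ 3 of 10". It then states: "Safety will be evaluated in 3 or 6 subjects at each dose level in the dose escalation component of the study". Section 8.4.2 refers the primary safety objective to this section, and Section 1.1.4 lists DLTs and the MTD or highest tested dose as the first primary endpoint.

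The other places that state the rule use six subjects to clear a level:

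- For Dose Level 1, Section 8.2 has: "If ≤ 1 of 6 patients experience a DLT, then the MTD will be declared, and initiation of the dose expansion phase will occur".
- Section 3.1.2, schema for Dose Level 1: "If ≤ 1 of the initial 6 subjects experience a DLT, dose expansion will commence". The same count applies at Dose Level -1.
- The Précis opens expansion at the same count, at most 1 of 6.

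In these places, a count of three appears in a decision only as an early stop for toxicity. Section 3.1.2 moves down a level on this condition: "If >1 of the initial 3 subjects, or if ≥ 2 of the 6 total subjects experience a DLT". Section 8.2 has the matching clause for the first three subjects at Dose Level -1.

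On numbers, Section 8.2 says: "Initial dose evaluation and or dose finding will require 6-12 subjects, followed by 4 additional subjects treated at a defined dose". The Précis and Sections 3.1.2 and 8.2 all give a total of 10 at the MTD. Some of the enrolment wording is looser: all three describe each level as having up to six patients, and Section 3.1.2 also speaks of 3 to 6 subjects in the initial component.

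**The concern.** Read on its own, Section 8.4.4 allows three DLT-free subjects to be enough to regard a level as safe. Read with the other sections, three subjects can fail a level but cannot clear it. These are different thresholds for the trial's main decision, in a combination that Section 1.2.8 says has not been tested in humans. A team that applied Section 8.4.4 literally could move on after three subjects. The evidence behind the declared dose would then be thinner than planned, the count at the expansion dose would miss the stated 10, and a dose above the 33% limit would pass somewhat more often.

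**Working it through.** **1. The plan's own figures reproduce.** The largest count x with x/n below 33% is:

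- n = 3: 0 (1/3 = 33.3% fails)
- n = 6: 1 (16.7%; 2/6 = 33.3% fails)
- n = 9: 2 (22.2%; 3/9 = 33.3% fails)
- n = 10: 3 (30.0%; 4/10 = 40.0% fails)

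The list in 8.4.4 is therefore arithmetically correct. The totals in 8.2 also reproduce: 6 + 4 = 10 at the MTD, and 12 + 4 + 16 screen failures = 32 enrolled.

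**2. The counts under each reading.** If six subjects are needed to clear a level, the stated minimum of 6 for dose finding and the total of 10 both follow. If 0 of 3 clears Dose Level 1, dose finding can end with 3 subjects, and 3 + 4 = 7 are treated at the expansion dose. The list in 8.4.4 has no entry for 7.

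**3. The chance of passing a level.** The documents give no true DLT rate p, so p is an assumption, taken over 20% to 60%.

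- Six-subject rule: P(X ≤ 1 of 6) = (1-p)^6 + 6p(1-p)^5. The early stop at 2 or more of the first 3 does not change this, because such a level already has at least 2 of 6.
- If 0 of 3 also clears, and 1 of 3 extends to six: (1-p)^3 + 3p(1-p)^2 × (1-p)^3. The extension is inferred: 1 of 3 is 33.3%, so not safe under 8.4.4, and it is not more than 1 of 3, so it does not trigger de-escalation under 3.1.2.
- The difference is the chance of 0 in the first three followed by 2 or 3 in the next three: (1-p)^3 × [3p^2(1-p) + p^3]. It is positive for every p between 0 and 1.

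At p = 0.33:

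- Six-subject rule: 0.0905 + 0.2673 = 0.358
- 0 of 3 also clears: 0.3008 + 0.4444 × 0.3008 = 0.434
- Difference: 0.3008 × 0.2548 = 0.077

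| Assumed true DLT rate | Six-subject rule | 0 of 3 also clears | Difference (points) |
|---|---|---|---|
| 20% | 65.5% | 70.9% | 5.3 |
| 30% | 42.0% | 49.4% | 7.4 |
| 33% | 35.8% | 43.4% | 7.7 |
| 40% | 23.3% | 30.9% | 7.6 |
| 50% | 10.9% | 17.2% | 6.3 |
| 60% | 4.1% | 8.2% | 4.1 |

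Differences are taken before rounding. The largest is about 7.7 points, near p = 36%. Below 33% the extra passes are of doses that meet the plan's own limit, so the cost lies in the rows from 33% upward.

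**4. Allowing for the check after expansion.** Suppose the level must also meet the 33% criterion once the 4 expansion subjects are in: at most 3 of 10, or at most 2 of 7 (2/7 = 28.6%), the latter being an assumed cut-off because the plan gives none. The chance of passing both steps, six-subject rule against 0 of 3 also clearing, is 32.8% v 38.7% at p = 33%, 19.9% v 25.4% at 40%, and 7.9% v 11.8% at 50%.

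**The case against.** The strongest reply is that Section 8.4.4 attaches no action to 0 of 3. It describes a level as safe; it does not say that expansion starts or that an MTD is declared. The action rules are in the Précis and Sections 3.1.2 and 8.2, and they agree on at most 1 of 6. The list also runs to 9 and 10, sizes that no dose-finding level reaches, and it follows a statement that DLTs are assessed continuously. It can therefore be read as running checkpoints for one criterion, with 0 of 3 meaning no need to de-escalate. Evaluation in three subjects could likewise refer to a level that stops early for toxicity.

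Most of this stands. A reader might infer that the plan authorises expansion after three subjects, or that only 7 will be treated at the expansion dose. No section says either, and the total of 10 is stated three times. A reader might also infer that the plan as written raises the chance of passing a too-toxic dose. That follows only under the sequence assumed in the working. If 0 of 3 were the only way to pass, the chance at 33% would be lower than under the six-subject rule (30.1% v 35.8%), and higher only above a true rate of about 44%.

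Confidence limits do not make the case stronger. The exact 95% upper limit is 71% after 0 of 3 and 46% after 0 of 6, but the six-subject rule also passes 1 of 6, where it is 64%.

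The reply does not remove the conflict. Section 8.4.4 never labels its list as checkpoints, and its next sentence but for that label sets evaluation at three or six subjects. The looser enrolment wording elsewhere does not settle the matter.

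**Conclusion.** The point holds as a conflict in a decision threshold. Section 8.4.4 treats 0 of 3 as safe and allows evaluation in three subjects, whereas the sections that carry the action rules need six subjects to clear a level, and the stated counts of 6-12 and 10 match them. The documents do not show that three subjects would in fact open expansion.

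The size is conditional. If 0 of 3 were used to clear a level and 1 of 3 extended to six, the chance of passing would rise by at most about 8 points: from 35.8% to 43.4% at an assumed true DLT rate of 33%, 23.3% to 30.9% at 40%, and 10.9% to 17.2% at 50%. Seven subjects rather than 10 would then be treated at the expansion dose. Monitoring during expansion, including the halting guidelines in Section 8.4.6.2, could catch some of these doses later, after more subjects have been treated. The effect is moderate, but it concerns the primary endpoint and is cheap to settle.

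**What to change.** Reconcile Section 8.4.4 with the Précis and Sections 3.1.2 and 8.2, so that one rule for clearing a dose level appears in all four places. Include the wording about up to six patients and about 3 to 6 subjects, because editing 8.4.4 alone would leave the same ambiguity elsewhere. The sponsor should state which rule applies, and whether the list in 8.4.4 is a clearance rule or a set of interim checkpoints. The rule should agree with the stated 6-12 dose-finding subjects and 10 at the MTD, or those counts should be restated.

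The cost is a few sentences across four places. If the sponsor confirms that six subjects are needed to clear a level, or that the list is only a set of checkpoints, the planned numbers do not change. If three subjects may clear a level, the sample-size text must change, and 8.4.4 needs a criterion for 7 subjects.

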3.1.1 Dose Limiting Toxicity

For the purposes of dose escalation a dose limiting toxicity (DLT) is defined as:

- Any Grade 3 or greater toxicity that is possibly related to the vaccine and as defined by Common Terminology Criteria for Adverse Events (CTCAE) Version 5.0 with the exception of transient (≤ 24 hours) Grade 3 flu-like symptoms or fever, which is controlled with medical management or transient (≤ 24 hours) Grade 3 fatigue, skin reactions or rash, headache, nausea, emesis that resolves to Grade ≤ 1 or asymptomatic grade 3 amylase/lipase elevation. For purposes of dose escalation the DLT evaluation period will be for 3 weeks following the first dose of drug.

Subjects experiencing a DLT will be removed from protocol therapy.

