3.7.2 Off-Study Criteria

- PI decides to end study
- Participant requests to be withdrawn from study. Reasons for withdrawal will be documented.
- Noncompliance with protocol guidelines (patient removed at discretion of Principal Investigator)
- Death
- Screen failure

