8.3 POPULATION FOR ANALYSES

Evaluable for toxicity: All patients will be evaluable for toxicity from the time of their first treatment with the combination ETBX-011, ETBX-051, ETBX-061 vaccine regimen.

Evaluable for objective response: Only those patients who have measurable disease present at baseline, have received at least one cycle of therapy, and have had their disease re-evaluated will be considered evaluable for response. These patients will have their response classified according to the definitions stated below. (Note: Patients who exhibit objective disease progression prior to the end of cycle 1 will also be considered evaluable.)

Evaluable Non-Target Disease Response: Patients who have lesions present at baseline that are evaluable but do not meet the definitions of measurable disease, have received at least one cycle of therapy, and have had their disease re-evaluated will be considered evaluable for non-target disease. The response assessment is based on the presence, absence, or unequivocal progression of the lesions.

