11 PHARMACEUTICAL INFORMATION

11.1 COMBINATION ETBX-011, ETBX-051, ETBX-061 VACCINE REGIMEN

The combination ETBX-011, ETBX-051, ETBX-061 vaccine regimen refers to the combination of three investigational adenoviral vaccines. All utilize the same second generation E1(-), E2 (-) vector. Subjects will each receive the three vaccines at the same time, at the same doses, through three separate injections administered in different limbs (proximal limb areas) or separate locations.

ETBX-011 is a CEA-targeting vaccine that comprises the Ad5 [E1-, E2b-] vector and a modified CEA (CEA(6D)) gene insert. The investigational product ETBX-061 is a MUC1-targeting vaccine that comprises the Ad5 [E1-, E2b-] vector and a modified MUC1 (MUC1c) gene insert. The investigational product ETBX-051 is a Brachyury-targeting vaccine that comprises the Ad5 [E1-, E2b-] vector and a modified Brachyury gene insert. (**Table 8**). Refer to the current version of the Investigator's Brochure for detailed investigational product information.

Table 8: Investigational Products

Table 8a

Product Name(s):	ETBX-011 (Ad5 [E1-, E2b-]-CEA(6D) Vaccine)
Dosage Form:	Suspension for injection

Dose	5 x 10 ¹¹ VP (standard dose), or 1 x 10 ¹¹ VP (DL-1).
Route of Administration	SC injection
Physical Description	ETBX vaccine is supplied as a sterile, clear solution in a 2-mL single-dose vial. The vaccine is provided at a concentration of 5 x 10 ¹¹ VP per 1 mL and contains ARM formulation buffer (20 mM TRIS, 25 mM NaCl, 2.5% glycerol, pH 8.0). Each vial contains approximately 1.3 mL of the vaccine. The product should be stored at -20+10°C until ready for use.
Manufacturer	Etubics

Table 8b

Product Name(s):	ETBX-061 (Ad5 [E1-, E2b-]-MUC1 Vaccine)
Dosage Form:	Suspension for injection
Dose	5 x 10 ¹¹ VP (standard dose), or 1 x 10 ¹¹ VP (DL-1).
Route of Administration	SC injection
Physical Description	ETBX vaccine is supplied as a sterile, clear solution in a 2-mL single-dose vial. The vaccine is provided at a concentration of 5 x 10 ¹¹ VP per 1 mL and contains ARM formulation buffer (20 mM TRIS, 25 mM NaCl, 2.5% glycerol, pH 8.0). Each vial contains 1 mL of extractable vaccine. The product should be stored at ≤ -60°C until ready for use.
Manufacturer	Etubics

Table 8c

Product Name(s):	ETBX-051 (Ad5 [E1-, E2b-]-Brachyury Vaccine)
Dosage Form:	Suspension for injection
Dose	5 x 10 ¹¹ VP (standard dose), or 1 x 10 ¹¹ VP (DL-1).
Route of Administration	SC injection

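### The dose-level decision counts all treated subjects, with no DLT-evaluable set or replacement rule, so a subject who goes off study inside the 3-week DLT period stays in the six, in effect as a non-DLT

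*Combined protocol and SAP*

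**What the plan says.** Section 8.4.4 calls a dose level safe when fewer than 33% "of subjects treated at a dose level experience a DLT", and adds: "A subject will be considered evaluable for safety if treated with at least one injection". Section 8.3 gives the only toxicity population: "All patients will be evaluable for toxicity from the time of their first treatment".

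The number of subjects per level is fixed by enrolment. Section 3.1.2 says "Up to six patients will be enrolled at dose level 1", and section 8.2 says "Up to six patients will be enrolled in an initial dose level 1". In both, at most one DLT among six opens the expansion phase.

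The observation period is given twice. Section 3.1.1 says: "For purposes of dose escalation the DLT evaluation period will be for 3 weeks following the first dose of drug". Section 8.4.4 says DLTs are observed for 1 week and allows the dose-level assessment from 1 week after the last subject's first injection.

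Section 3.7.2 lists the ways off study, among them "Participant requests to be withdrawn from study", removal for noncompliance, and death. Section 6.1 follows adverse events for at least 30 days after treatment stops, or until off-study if that comes first.

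**The concern.** The plan sets evaluability conditions for its other outcomes. Section 8.3 requires treatment and a re-evaluation for response, and section 8.4.9 requires at least three vaccine injections for immune response. The count that selects the dose has no such condition: no minimum observation time and no replacement rule. Because the cap applies to enrolled patients, a subject lost early cannot be replaced under the text as it stands.

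Such a subject may be largely unobserved. After week 0 the study calendar (3.5) schedules no visit, chemistry, blood count or diary review until week 3. A subject off study before then has no scheduled post-dose laboratory values, and adverse event follow-up has ended under 6.1. The safety visit in 3.7 is due within 90 days, so it does not secure contact by week 3.

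The decision at stake is the primary one: opening expansion and, with it, the recommended phase 2 dose. The error runs one way, since an unseen DLT can only lower the count. Without a rule, the team would have to settle how to treat an early loss after the DLT results are known.

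**Working it through.** **The plan's own figure.** Section 8.2 gives up to 12 dose-finding subjects, 4 in expansion and 16 screen failures: 12 + 4 + 16 = 32. This reproduces the stated ceiling and includes no allowance for replacements.

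**Inputs from the documents.** Pass rule: at most 1 DLT of 6 (3.1.2, 8.2). Reference DLT rate: 1/3, close to the 33% limit in 8.4.4. The early stop at two DLTs in the first three does not alter the pass probability, because two of three already means at least two of six.

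**Assumptions.** The documents give neither a true DLT rate nor a loss rate. I take a loss rate q of 3%, range 1% to 5%, and score a lost subject as a non-DLT with no observation from day 0.

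**Pass probability given the number observed.** With m of the six observed and DLT rate p, P(pass) = (1−p)^m + m·p·(1−p)^(m−1). At p = 1/3:

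| Observed among the six | P(pass) |
|---|---|
| 6 | 64/729 + 192/729 = 256/729 = 35.1% |
| 5 | 32/243 + 80/243 = 112/243 = 46.1% |
| 4 | 16/81 + 32/81 = 48/81 = 59.3% |

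One loss adds 46.1 − 35.1 = 11.0 points.

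**Average over random losses.** Each of the six counted subjects shows a DLT with probability p(1−q), so P(pass) is the same formula with m = 6 and that rate.

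| True rate p | No loss | q = 1% | q = 3% | q = 5% |
|---|---|---|---|---|
| 1/3 | 35.1% | 35.8% | 37.1% | 38.5% |
| 50% | 10.9% | – | 12.4% | – |
| 10% | 88.6% | – | 89.2% | – |

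**How often a loss occurs at q = 3%.** At least one among six: 1 − 0.97^6 = 16.7%. Two or more: 1.2%.

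**Room for replacements.** Expected replacements per six-subject level at 3% loss: 6 × 0.03/0.97 = 0.19. If level 1 passes, 6 + 4 + 16 = 26, leaving 6 of the 32 places. If both levels fill and all 16 screen failures occur, none are left.

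**The case against.** The strongest reply is that few subjects are affected. Anyone who only progresses or stops treatment is still followed for at least 30 days under 6.1, and the week-3 visit closes the window for everyone still on study. What remains is complete departure from the study within 3 weeks of a first vaccination, which is probably rare. A subject who leaves in week 2 or 3 has already contributed much of the observation; section 3.6 expects local reactions over several days. Under the 1-week window of 8.4.4 the problem would nearly disappear. Section 7.6.1 also has the team discuss each patient weekly, so the count need not be mechanical. All of this stands as to size. None of it supplies an evaluability or replacement rule, and the 1-week window conflicts with 3.1.1.

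Three stronger readings are tempting, and the documents do not support them.

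- *A subject given only one of the three vaccines is plainly admitted.* Section 11.1 does say "Subjects will each receive the three vaccines at the same time, at the same doses, through three separate injections". Elsewhere, however, injection usually means a vaccination occasion. Section 8.4.4 equates it with a treatment, and 3.2 times vital signs by first and subsequent injections. The three-injection minimum in 8.4.9 would be empty if it counted needle-sticks, since one complete visit would meet it. Section 3.4 also bars dose modifications.
- *Any early death hides a DLT.* A death possibly related to vaccine is itself a DLT under 3.1.1 and suspends injections under 8.4.6.2. Only an unrelated death cuts observation short without being counted.
- *The plan says that unobserved subjects are DLT-free.* It does not. That follows from the treated-subject denominator together with silence on incomplete observation.

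**Conclusion.** The point holds for subjects who go off study inside the 3-week period. The all-treated set is right for adverse event tables; the defect is that it is also the only set offered for the dose decision, with a cap of six and no replacement. The bias can only favour passing the level.

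The size is small on average: about 2 points at a true DLT rate of 1/3 with an assumed 3% loss, 1.5 points at a rate of 50%, and 0.6 points at 10%. A reader might take the 11-point effect of one loss as typical. It is not: under the same assumption a loss among the six has about a 17% chance of occurring, and the 11 points are an upper bound. The average figures rest on the same day-0 scoring and on a loss rate that the documents do not give.

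The halting rules in 8.4.6.2 and the threshold of 3 in 10 in 8.4.4 limit later harm but do not correct the decision to open expansion. Severity is minor to moderate and confidence moderate: a cheap improvement to a rule that serves the primary endpoint.

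**What to change.** 1. In 8.3 and 8.4.4, keep the all-treated set for adverse event tabulation and add a DLT-evaluable set for the dose decision. A subject belongs to it if they had a DLT, or received the full three-vaccine first dose and were observed for the full 3 weeks of 3.1.1. The full-first-dose condition is a precaution only.
2. In 8.4.4, replace the 1-week observation and decision timing with the 3-week period.
3. In 3.1.2 and 8.2, make the cap *up to six DLT-evaluable patients* and state that non-evaluable subjects are replaced within the ceiling of 32.

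The cost is wording in four sections, an occasional extra treated subject and slightly longer accrual at that level. The ceiling can stay as it is; it is tight only if both levels fill and all 16 assumed screen failures occur.
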